
Assessment methods
	
1. Efficacy assessment
 
1) Endpoints of main interest
 
 ① Number of patients with complete healing# of ulcer within 12 weeks ② Time to complete healing of ulcer within 12 weeks ③ Pressure ulcer size reduction rate based on using a scale at each time point 
# The definition of complete healing Epithelial tissue covering 100% of the study ulcer, no abrasion or ulceration, intact dermis and epidermis
 
2) Other endpoints
 
 ① The PUSH(Pressure Ulcer Scores for Healing) reduction rate from baseline to each time point ② Dressing change frequency during the entire period ③ Number of subjects with Early completion due to complete healing during the study ④ Incidence of new infections at the pressure ulcer until Week 12 based on the CSSC 
2. Safety assessment
 
 ◆ Vital signs, laboratory tests ◆ Local adverse events at the target pressure ulcer: Erythema, edema, itching, flare, rash, other ◆ Other adverse events

Statistical analysis methods
	
Efficacy is assessed in the FAS while safety is evaluated in the SS.
 
 - SS(Safety set): Subjects who had at least 1 application of the investigational device and had at least 1 safety assessment - FAS(Full analysis set): Subjects who had at least 1 application of the investigational device and then had at least 1 available endpoints of main interest review 
1. Efficacy assessment
 
1) Endpoints of main interest
 
Of Endpoints of main interest, for subjects achieving complete healing within 12 weeks, present frequency and percentage.
 
For the time to 100% complete healing, analyze using the Kaplan-Meier method. Subjects not achieving 100% complete healing within 12 weeks will not be

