	
considered for evaluation for end point of main interest. For the pressure ulcer size reduction rate by group, present mean and standard deviation.
 
2) Other endpoints For other endpoints, present mean and standard deviation for continuous variables ①, and frequency and percentage for categorical variables ②, ③, ④.
 
2. Safety assessment
 
1) Adverse events List all adverse events that occurred by group. Record the frequency of adverse events related or unrelated with the investigational device by group. For the number of adverse events and the percentage of subjects who had at least 1 adverse event, present the 95% confidence interval in each treatment group. Analyze adverse events separately for local adverse events at the target pressure ulcer and other adverse events.
 
2) Laboratory test findings For continuous data, present descriptive statistics (mean, standard deviation, median, minimum, maximum) by group and time point. In addition, tabulate the proportion of normal/abnormal results by time point in each group.
 
3) Vital signs For continuous variables, present descriptive statistics (mean, standard deviation, median, minimum, maximum) for the baseline and end-of-study test findings by group and time point.

--	--

▣ Schedule of study activities

Item \ Schedule	Screening		Treatment period																				Closing			
	1*	2*	3	4	5	6	7	8	9	10	11	12	13	14**												
	-14d~0d	1d 5d* (±1d)	8d (±1d)	12d* (±1d)	15d (±1d)	19d* (±1d)	22d (±1d)	26d* (±1d)	29d (±1d)	33d* (±1d)	36d (±1d)	40d* (±1d)	43d (±1d)	47d* (±1d)	50d (±1d)	54d* (±1d)	57d (±1d)	61d* (±1d)	64d (±1d)	68d* (±1d)	71d (±1d)	75d* (±1d)	78d (±1d)	82d* (±2d)	85d (±2d)	
Informed Consent Form	V																									
Demographic/medical history review	V																									
Physical examination	V	V	V	V	V	V	V	V	V	V	V	V	V	V	V	V	V	V	V	V	V	V	V	V	V	V
Vital signs ¹	V		V	V	V	V	V	V	V	V	V	V	V	V	V	V	V	V	V	V	V	V	V	V	V	V
Laboratory tests ²	V																									V
Height	V																									
Body weight	V							V																		V
Pregnancy test ³	V						V																			
Inclusion/exclusion criteria review	V	V																								
Randomization		V																								
Investigational device application ⁴		V	V	V	V	V	V	V	V	V	V	V	V	V	V	V	V	V	V	V	V	V	V	V	V	V
Investigational device prescription ⁵		V	V	V	V	V	V	V	V	V	V	V	V	V	V	V	V	V	V	V	V	V	V	V	V	V

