Among 80 burn patients who received a split-thickness skin graft, half of the grafted donor sites were covered with Medifoam N and the other half were covered with Vaseline gauze dressings. Two days after the procedure, dressings were removed, and it was monitored everyday whether epithelization occurred or any complication developed. Results indicated that it took an average of 10.1 days in the Medifoam N group and 13.0 days in the control group, and 80 subjects recovered with no serious complications.

(2) Medifoam Silver

Medifoam Silver was investigated for the effectiveness in re-epithelization in 31 patients with 2- or 3-degree burns with a wound area of 12.6% and 24 patients with a skin graft donor site and a wound area of less than 1.000 cm². In 27 burn patients, re-epithelization was achieved in mean 18.6 days (5-29 days). In 4 patients, it took mean 14.3 days (12-18 days) until an eschar fell off. In 24 patients with a skin graft donor site, successful re-epithelization was achieved after mean 9.5 days (7-15 days) following skin graft. During this period, no complication or side effect occurred and exudates were absorbed well.

This medical device is registered product and currently in use for burn, skin graft, lacerated skin, surgical wound as well as pressure ulcer in clinical field. Clinical trials in burn, skin graft, wound, surgical wound have been done and confirmed the efficacy among those indications. However, clinical trial data on pressure ulcer is not adequate (refer to 8. BETAplast™ PRODUCT MONIGRAPH on protocol reference 24). Therefore, this pilot study is designed to figure out the efficacy of this device on pressure ulcer and additional clinical trial will be conducted upon using the result of this study.

(3) Medifoam H

Medifoam H and DuoDERM were used for 7 days on 66 various wounds including laceration, abrasion, mild burn, and surgical wounds. In some patients, Medifoam H caused mild pruritus when compared to DuoDERM. In terms of exudate improvement, both groups achieved improvement, and the extent of improvement from baseline (pre-dressing) was 82% for Medifoam H and 67% for DuoDERM.

Based on these results, it was planned to apply each of Medifoam[®] and Betafoam[®] to subjects with pressure ulcer, and exploratively observe efficacy of two study devices at the pressure ulcer.

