15.1 General principles of result analysis

Data obtained from subjects in this study will be analyzed as the SS(Safety Set) and the FAS(Full Analysis set).

- 1) In the SS(Safety set), data obtained from subjects who were enrolled in the study, had at least

- 1 application of the study device, and had at least 1 safety assessment will be analyzed.
- 2) In the FAS(Full analysis set), data obtained from subjects who were enrolled in the study, had at least 1 application of the study device and then had at least 1 available endpoints of main interest review will be included in analysis.

Efficacy and demographics will be analyzed using the FAS and safety data will be analyzed using the SS.

For subjects with a missing value during the study or who are withdrawn from the study prior to study completion, efficacy analysis will be conducted by applying the LOCF (Last Observation Carried Forward), only in case such subjects have available endpoints of main interest assessment results after the investigational device application. However, in case of missing values for Other endpoints and safety endpoints, raw data will be used for analysis, without applying LOCF.

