#### - Criteria for discontinuation of the study device application

- 1) Acute reactions (allergy, hypersensitivity reactions, etc.) to the study device
- 2) It is determined that continuation of the study is difficult due to an accidental intercurrent condition.
- 3) It is determined that continuation of the study is impossible due to worsening of the pressure ulcer (Stage 4 or higher).
- 4) Debridement was performed during the study, after the study device application.
- 5) Pregnant during the study period
- 6) It is otherwise determined by the investigator that continued application of the study device is not appropriate due to reasons such as serious malnutrition, etc.
- 7) It is determined by the investigator that study participation is not appropriate due to a "serious adverse event".

"Serious adverse event" is an event, irrespective of a causal relationship with the study device, that is as follows:

- ① Results in death or is life-threatening
- ② Requires inpatient hospitalization or prolongation of existing hospitalization

- ③ Results in persistent or significant disability or dysfunction
- ④ Results in congenital anomaly or birth defect
- ⑤ Other medically important event as identified by the Investigator

In case of discontinuation due to worsening of a pressure ulcer, the treating physician will ensure safety of the patient with appropriate tests and treatment, equivalent to the case of an adverse event.

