### Analysis of Efficacy Endpoints

#### (1) Analysis of endpoints of main interest

- ① For subjects achieving complete healing within 12 weeks, present frequency and percentage. Fisher's exact test will be performed to compare Medifoam and Betafoam treatment groups.
- ② For the time to 100% complete healing, analyze using the Kaplan-Meier method. Time table for subjects to 100% complete healing will be presented and the survival Plot will be shown as a figure. Subjects not achieving 100% complete healing within 12 weeks will not be considered for evaluation for end point of main interest though ulcer size reduction will be evaluated for those subjects.

- ③ For the pressure ulcer size by each time point, present the mean, median, min, max and standard deviation. t-test will be conducted to compare Medifoam and Betafoam, and paired t-test will be used to see the difference between each post visit and baseline(1d).
- ④ For the pressure ulcer size reduction rate, present the mean, median, min, max and standard deviation. t-test will be conducted to compare Medifoam and Betafoam.
- ⑤ For the analysis for efficacy, conduct sub-analyses by use of topical antibiotics and glucocorticoids for the pressure ulcer during the study. t-test will be performed to compare Medifoam and Betafoam, and paired t-test will be used to see the difference between post visits and baseline(1d).

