## 9. Handling Missing Values

---

---

For subjects with a missing value during the study or who are withdrawn from the study prior to study completion, efficacy analysis will be conducted by applying the LOCF (Last observation Carried Forward), only in case such subjects have available endpoints of main interest assessment results after the investigational device application. However, in case of missing values for other endpoints and safety endpoints, raw data will be used for analysis, without applying LOCF.

---

---

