#### 4) Medication History

Analysis Set: FAS

Table 0401 Prior/Concomitant Medication

		Medifoam	Betafoam	Total	P-value
		n(%)	n(%)	n(%)	
Prior Medication	Yes	xx(xx.xx%)	xx(xx.xx%)	xx(xx.xx%)	0.xxxx‡
	No	xx(xx.xx%)	xx(xx.xx%)	xx(xx.xx%)	
	Total	xx(xx.xx%)	xx(xx.xx%)	xx(xx.xx%)	
Concomitant Medication	Yes	xx(xx.xx%)	xx(xx.xx%)	xx(xx.xx%)	0.xxxx‡
	No	xx(xx.xx%)	xx(xx.xx%)	xx(xx.xx%)	
	Total	xx(xx.xx%)	xx(xx.xx%)	xx(xx.xx%)	

‡: Fisher's exact test

Table 0402 Prior Medication in detail((Level1/Level3) of WHO ATC\*)

		Medifoam		Betafoam		Total	
		n	(%)	n	(%)	n	(%)
Total		xx	(xx.xx)	xx	(xx.xx)	xx	(xx.xx)
Level1	Level3	xx	(xx.xx)	xx	(xx.xx)	xx	(xx.xx)
	Level3	xx	(xx.xx)	xx	(xx.xx)	xx	(xx.xx)

Note) \* Coded in WHO ATC Class

Table 0403 Concomitant Medication in detail ((Level 1/ Level 3) of WHO ATC\*)

		Medifoam			Betafoam			Total		
		n	(%)	freq	n	(%)	freq	N	(%)	freq
Total		xx	(xx.xx)	xx	xx	(xx.xx)	xx	xx	(xx.xx)	xx
Level1	Level3	xx	(xx.xx)	xx	xx	(xx.xx)	xx	xx	(xx.xx)	xx
	Level3	xx	(xx.xx)	xx	xx	(xx.xx)	xx	xx	(xx.xx)	xx

Note) Percentage is based on FAS Set subjects within each column.

Note) \* Coded in WHO ATC Class

5) Pressure ulcer assessment at Screening(Visit1)

Table 0501 List of body parts where pressure ulcer occurred

	Medifoam	Betafoam	Total
Body Part	n	n	n
Location1	xx	xx	xx
Location2	xx	xx	xx
Location3	xx	xx	xx
Location4	xx	xx	xx
...	xx	xx	xx
Total	xx	xx	xx

Table 0502 Pressure ulcer size at Screening

Measurement		Medifoam	Betafoam	Total	P-value
Length(cm)	N	xx	xx	xx	0.xxxx*
	Mean±Std	xx.xx±x.xx	xx.xx±x.xx	xx.xx±x.xx	
	Median	xx.xx	xx.xx	xx.xx	
	Min~Max	xx.xx~xx.xx	xx.xx~xx.xx	xx.xx~xx.xx	
Width(cm)	N	xx	xx	xx	0.xxxx*
	Mean±Std	xx.xx±x.xx	xx.xx±x.xx	xx.xx±x.xx	
	Median	xx.xx	xx.xx	xx.xx	
	Min~Max	xx.xx~xx.xx	xx.xx~xx.xx	xx.xx~xx.xx	

6) Analysis of endpoints of main interest

Analysis Set: FAS

Table 0601 Number of patients with complete healing of ulcer within 12 weeks

		Medifoam	Betafoam	Total	P-value
		n(%)	n(%)	n(%)	
Complete healing of ulcer within 12 weeks	Yes	xx(xx.xx%)	xx(xx.xx%)	xx(xx.xx%)	0.xxxx‡
	No	xx(xx.xx%)	xx(xx.xx%)	xx(xx.xx%)	
	Total	xx(xx.xx%)	xx(xx.xx%)	xx(xx.xx%)	

‡: Fisher's exact test

Table 0602 Time taken for subjects to reach complete healing of ulcer within 12 weeks(in days)

		Medifoam	Betafoam	Total	P-value
Time(days)	N	xx	xx	xx	0.xxxx*
	Mean±Std	xx.xx±x.xx	xx.xx±x.xx	xx.xx±x.xx	
	Median	xx.xx	xx.xx	xx.xx	
	Min~Max	xx.xx~xx.xx	xx.xx~xx.xx	xx.xx~xx.xx	

Note) \*: t-test, ¥ : Wilcoxon rank sum test

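### The Kaplan-Meier analysis of time to complete healing drops subjects unhealed at week 12 instead of censoring them, so Table 0602 and Figure 0601 cannot show which dressing heals faster

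*SAP*

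**What the plan says.** Time to complete healing within 12 weeks is an endpoint of main interest (Protocol 16.1, SAP 7.1), counted in days from baseline.

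- **Method.** SAP section 8, endpoints of main interest, item 2, names Kaplan-Meier, a time table and a survival plot. It then says: "Subjects not achieving 100% complete healing within 12 weeks will not be considered for evaluation for end point of main interest". The sentence ends by saying that these subjects are still evaluated for ulcer size reduction.
- **Same rule elsewhere.** Protocol 15.3 and the synopsis (Statistical analysis methods) repeat the exclusion. The synopsis reads "Subjects not achieving 100% complete healing within 12 weeks will not be" and continues "considered for evaluation for end point of main interest".
- **Output.** SAP Table 0602 is titled "Time taken for subjects to reach complete healing of ulcer within 12 weeks(in days"). Its rows are N, mean and SD, median and range, with a t-test or Wilcoxon p-value. It has no row for censored subjects. Figure 0601 is listed as a Kaplan-Meier plot by arm; its mock-up is not visible in the text available.
- **Analysis set.** Protocol 15.1: "Efficacy and demographics will be analyzed using the FAS and safety data will be analyzed using the SS". Membership of the FAS does not require healing.
- **Withdrawals.** SAP section 9: "efficacy analysis will be conducted by applying the LOCF (Last observation Carried Forward"), for the endpoints of main interest. Neither document gives a censoring rule for a subject who is unhealed at day 85 or who leaves earlier.

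**The concern.** Kaplan-Meier is used because some subjects do not have the event during follow-up. They stay in the risk set until censored and hold the curve down. If they are removed, every subject left has the event, so each curve ends at 100% healed in both arms. The output then describes how quickly healers healed. It does not describe how quickly ulcers heal on a dressing.

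The comparison is also conditional on an outcome observed after randomisation. An arm in which 2 of 10 heal early would look better in Table 0602 and Figure 0601 than an arm in which 7 of 10 heal spread over 12 weeks, while Table 0601 would show 20% against 70%.

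The trial is an exploratory pilot with no decision rule, so the harm is a misleading curve, median and p-value on one of its main endpoints. Protocol 5.1 adds that an "additional clinical trial will be conducted upon using the result of this study". A healers-only time could therefore be carried into later planning, though the documents do not say which results will be used.

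**Working it through.** **Inputs.** From the documents: 10 subjects per arm (Protocol section 9) and 12 weekly assessments from 8d to 85d, that is 84 days after baseline (Protocol 10.1). The plan states no healing rate, power or event count, so there is no figure of its own to reproduce. The healing probabilities p below are assumptions, with exponential healing times.

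**1. What the rule yields in principle.** With a daily healing rate λ = −ln(1 − p)/84:

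- median in all subjects = ln 2/λ
- median among those healed by day 84 = −ln(1 − p/2)/λ

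For p = 0.20, λ = 0.2231/84 = 0.002656. The all-subject median is 0.6931/0.002656 = 260.9 days, and the healers-only median is 0.1054/0.002656 = 39.7 days.

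| Healed by week 12 | All-subject median (days) | Healers-only median (days) |
|---|---|---|
| 10% | 552.6 | 40.9 |
| 20% | 260.9 | 39.7 |
| 30% | 163.2 | 38.3 |
| 60% | 63.5 | 32.7 |
| 80% | 36.2 | 26.7 |

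In practice any median beyond day 84 would be reported as not reached. For 20% against 60%, the correct report is not reached against 64 days; the planned one is 39.7 against 32.7 days.

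**2. How often the planned output points the wrong way.** Take 10 per arm, with times rounded up to the next weekly visit. The chance that both arms have at least one healer is (1 − (1 − p₁)¹⁰)(1 − (1 − p₂)¹⁰). For 20% against 60% this is 0.8926 × 0.9999 = 89.3%. The last two columns are among trials with a healer in both arms.

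| True 12-week healing | Healer in both arms | Better arm's healers have equal or longer mean time | Better arm has no more healers than the other |
|---|---|---|---|
| 20% vs 60% | 89% | 42% | 5% |
| 30% vs 60% | 97% | 43% | 12% |
| 30% vs 80% | 97% | 32% | 1% |
| 20% vs 80% | 89% | 34% | 0.3% |

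Exact ties in the mean make up only 1.1% to 1.6%. The last column is the corresponding error in Table 0601, which rarely misleads.

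**3. A constructed data set.** One arm heals 3 of 10 (days 22, 29, 36). The other heals 8 of 10 (days 22, 29, 36, 50, 57, 64, 71, 78).

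- *Everyone included, unhealed censored at day 85:* 30% against 80% healed. The median is not reached in the first arm and lies between days 57 and 64 in the second, where exactly half are healed. Log-rank p = 0.066, favouring the arm with 8 healers.
- *Plan as written:* both curves reach 100%. Means are 29.0 against 50.9 days and sample medians 29 against 53.5 days; t-test p = 0.11. The direction favours the arm with 3 healers.

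**4. Withdrawals.** Take one arm of 10: three heal (days 29, 50, 71), two discontinue for worsening (last assessed on days 22 and 36), and five are unhealed at day 85.

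- *As written:* 100% healed.
- *Both withdrawals censored at last assessment:* 1 − (8/9)(6/7)(5/6) = 36.5%.
- *Both counted as not healed through day 85:* 3/10 = 30%, which agrees with Table 0601.

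Most of the error comes from the exclusion. The handling of withdrawals is a smaller, second question.

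**The case against.** **The text could be read more kindly.** Figure 0601 cannot be seen, and a programmer who is told to use Kaplan-Meier might take the sentence to mean that the unhealed are not events, and censor them at day 85. That is possible, but neither document says it. The end of the SAP sentence sends these subjects to the ulcer size analysis instead, and Table 0602 can be filled only for subjects who have a healing day. The conclusion about the figure rests on the text alone.

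**Table 0602 is legitimate as a description.** This stands in part: a summary of healers' times is acceptable if labelled as such. The fault is the between-arm p-value and the missing label. SAP section 8, item 2, names no test for this endpoint, and Protocol 16.2 says no formal test will be done, so the p-value appears only in the table shell.

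**The FAS conflict is weak.** The exclusion can be seen as an evaluability rule for one endpoint within the FAS. This is fair, and the point does not depend on it.

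**It is a pilot of 20 subjects, and Table 0601 sits alongside.** This limits the harm to misleading exploratory output. It does not make the curve or median correct.

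**The sizes are assumed.** They are, and the simulated differences are large (30 to 60 percentage points). They show the mechanism and do not predict this trial's results.

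**The handling of discontinuations is a choice of estimand.** This stands. Inclusion with a stated censoring rule is the essential correction; other treatments of discontinuation can be defended.

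**Conclusion.** The concern holds. Followed as written, the plan yields a time-to-healing curve that must end at 100% in both arms and a p-value on subsets defined by the outcome. That both curves reach 100% follows from the rule itself and needs no assumption about healing rates. The sizes do need one: under exponential healing, and given a healer in both arms, the better arm's healers have an equal or longer mean time in 32% to 43% of the simulated scenarios' trials.

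The defect is confined to Table 0602 and Figure 0601. Table 0601 keeps the unhealed in its denominator, and the ulcer size analyses include them. It should be corrected before analysis, because the endpoint is one of main interest and the correction is cheap.

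**What to change.** **Essential**

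- Delete the exclusion sentence in SAP section 8 item 2, Protocol 15.3 and the synopsis, keeping the SAP's statement that ulcer size reduction is evaluated in unhealed subjects.
- Include all FAS subjects. The event is the first visit at which complete healing is recorded. Censor unhealed completers at the day-85 assessment, and subjects lost for reasons unrelated to the ulcer at their last ulcer assessment.
- State that LOCF does not apply to this endpoint.
- In Figure 0601 and its table, report cumulative healing at week 12 with a 95% confidence interval, numbers at risk, and the median if reached.
- Drop the Table 0602 p-value and label the table as a description of healers only.

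**Recommended choice of estimand**

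Some discontinuations carry information about healing; one listed criterion in SAP section 5 is "It is determined that continuation of the study is impossible due to worsening of the pressure ulcer (Stage 4 or higher"). Count death and discontinuation for worsening, debridement or a serious adverse event as not healed through day 85, or treat them as competing events. Use censoring at the last assessment as a sensitivity analysis. The week-12 estimate then equals the Table 0601 percentage unless someone is lost for an unrelated reason.

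**Cost**

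Wording edits in three places, with IRB approval of the protocol change (Protocol 21.2), and one reprogrammed table and figure. No new data are needed: healing status is recorded weekly and discontinuation reasons are already in the Case Report Form. Reported healing times will look less favourable, and the median may be not reached.

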## **(2) Analysis of other endpoints**

For other endpoints, present the mean, median, min, max and standard deviation for the continuous variable PUSH reduction rate at each time point, and frequency and percentage for categorical variables of Dressing change frequency, Number of subjects with early completion due to complete healing, and Incidence of new infections at the pressure ulcer after investigational device application. t-test and paired t-test will be conducted for PUSH reduction rate while Fisher's exact test will be used to see the difference between Medifoam and Betafoam for Dressing change frequency, Number of subjects with early completion, and Incidence of new infections.

